NCT03061903

STUDY TITLE

Closed Incision Negative Pressure Therapy vs. Standard of Care for Surgical Incision Management in High-Risk Patients following Total Hip Arthroplasty: A Randomized Controlled Trial

DOCUMENT DATE: 10/22/2012

Version Date: Page 1 of 6

RESEARCH PROTOCOL

STUDY TITLE

Closed Incision Negative Pressure Therapy vs. Standard of Care for Surgical Incision Management in High-Risk Patients following Total Hip Arthroplasty: A Randomized Controlled Trial

Investigators

[name], Assistant Professor of Orthopedic Surgery (Principal Investigator)

Study Coordinator

[name]
[contact]
[contact]

Lead Institution

Center for Hip & Knee Replacement Department of Orthopaedic Surgery Columbia University Medical Center [contact]

INTRODUCTION

Direct anterior approach (DAA) for total hip arthroplasty (THA) is becoming increasingly popular, with an estimated 25% of all procedures being performed through this approach in the United States. However complications have been reported such as an increased risk of wound complications and surgical site infections. Jewett et al¹ cited having a 4.6% wound complication rate with this approach. Christensen et al² also reported 1.4% of their direct anterior approach total hips replacements required reoperation for wound complications versus 0.2% of their posterior approach hips. Using stricter criteria to define wound complications, we have recently published a retrospective analysis of 651 consecutive DAA hips,³ identifying an 11.5% wound complication rate and a 1.9% reoperation rate for these wound complications.

Risk factors for surgical site infections and prosthetic joint infections have been studied in the arthroplasty population. Many have been identified and include morbid obesity and increased comorbidities such as diabetes. ^{4,5,6} In our retrospective study,³ we have specifically identified BMI > 30 kg/m², the presence of diabetes, active smoking status, and previous hip surgery as risk factors for wound complications and reoperation. Based on preliminary data, we documented a 31% wound complication rate in this "high-risk" subset of patients using standard-of-care dressings and incision management. This rate is unacceptably high for a common elective operation, prompting the desire to investigate alternative therapies.

Closed incision negative pressure therapy (ciNPT) has been used for the treatment and prevention of incisional complications. More recently, studies have reported results of ciNPT over the closed incision for prevention of postoperative wound complications. Karlakki et al⁷ reviewed the literature regarding this application in orthopaedic surgery and showed reports of decreases in wound hematoma, drainage, and infection. Most of these reports were of patients that sustained high-energy traumatic injuries. Other studies also show similar support of ciNPT for closed cardiothoracic, abdominal, plastic, and vascular incisions. We have recently published results of a retrospective investigation examining 138 patients undergoing revision hip and knee arthroplasty procedures. In this study, we found significant decreases in wound complications (7% vs. 27%) and surgical site infections (3% vs. 19%) with ciNPT.⁸ Based on this study, many surgeons in the US have adopted ciNPT as their standard of care in revision arthroplasty procedures. To our knowledge, few additional studies have examined ciNPT application in the arthroplasty population and none have focused its use in prevention of wound complications in the primary total hip arthroplasty population undergoing surgery through the DAA.

We propose a prospective, randomized controlled trial to examine the utility of ciNPT for incision management in the at-risk patient population following THA performed through the direct anterior approach.

OBJECTIVE(S)/SPECIFIC AIMS AND HYPOTHESES

 To evaluate the potential effects of ciNPT on reduction of overall wound complications following DAA THA in high-risk patients.

Version Date: 10/22/12 Page 2 of 6

To evaluate the potential effects of ciNPT on reduction of reoperation following DAA THA in highrisk patients.

Null hypotheses:

• In the at-risk patient population, there is no difference in 1) the overall wound complication rate, and 2) the rate of reoperation for wound complications, between the standard incision management group and the group where ciNPT is used to aid incision management.

EXPERIMENTAL DESIGN

The goal of this study is to determine the efficacy of ciNPT for prevention of wound complications and return to the operating room for wound complications in patients with pre-determined risk factors that affect wound healing (BMI > 30kg/m², diabetes mellitus, smoking, history of prior hip surgery). This is will be a prospective, randomized, controlled trial. Inclusion criteria will be patients undergoing DAA THA by the investigating surgeons that have at least one risk factor for complicated wound healing as described above, based on previous retrospective data. Subjects will be randomly assigned to either the ciNPT intervention group or the control group using computer-generated, randomized envelopes with equal numbers in each treatment arm. Both dressings will be applied under sterile conditions at the end of the DAA THA surgery, while still in the operating room, and then removed after 7 days.

Patients randomized to the control group will receive a conformable, water resistant, silver-impregnated, antimicrobial hydrofiber dressing (AQUACEL® Ag, Convatec) which is currently the standard of care at our institution for postoperative wound dressing. This dressing is left in place for 7 days and then removed by the patient or visiting nurse at home. Patients randomized to the study group will receive an incisional ciNPT device, which is currently being used selectively in high-risk patients at our institution (Prevena™, KCI). Both wound dressings are FDA-approved devices. Due to the obvious difference in appearance of the two dressings, neither patients nor treating surgeons can be blinded to treatment arm.

Wounds will be assessed postoperatively at regular intervals until wound healing is achieved. This will occur at least 2 and 6 weeks after surgery, which are standard intervals in our current postoperative protocol. No additional office visits will be needed for patients in the control or treatment arms. Photodocumentation of the wounds will occur at two and six weeks postoperatively. Primary outcome measure will be uneventful wound healing (requiring no intervention) versus the occurrence of wound complications (wound drainage, breakdown, necrosis, dehiscence, superficial or deep infection) requiring additional intervention. Intervention will be defined as any attempt of the surgeon to improve wound healing (in-office debridement, topical ointment, aspiration, antibiotic therapy, or return to the OR for the wound). Secondary outcome measures will include duration of wound healing delay, length of hospital stay, number of days of antibiotic therapy, and direct and estimated indirect costs. Statistical analysis will be performed to detect differences in the treatment groups

An *a priori* sample size calculation was performed based on data from our pilot study and from the existing literature. Currently, our retrospective data indicates wound complications should occur in approximately 31% of our "high risk" patients in the control group. We do not have reliable retrospective data for the study ciNPT group, so we are assuming a 4.57 relative risk reduction in wound complications using the ciNPT device based on existing data in the literature. An intention-to-treat analysis will be used. Given the short-term nature of this study, our expected dropout rate is very close to zero (and will in all likelihood be zero). Assuming an ITT analysis, any dropouts should be counted as failures. With an estimated dropout rate of 5%, the incidence of wound complications in the control group would be 34.5% and the incidence of wound complications in the ciNPT group would be 11.5%. Our assumptions include an equality analysis, 2-sided p-value < 0.05, and Fisher's exact test. Using these baseline assumptions, 116 patients (58 per group) will be required to achieve 80% power.

Based on our pilot study, 37% of our patient population should meet our inclusion criteria. Patients will need to be followed for at least 90 days to assess postoperative wound healing complications.

INCLUSION AND EXCLUSION CRITERIA Subject Selection

Version Date: 10/22/12 Page 3 of 6

Prospective inclusion criteria:

- 1. Patients undergoing primary THA through a direct anterior approach by one of the investigating surgeons
- 2. The presence of one or more of these risk factors for delayed or problematic wound healing:
 - a. Diabetes
 - b. Obesity (BMI > 30)
 - c. Active smoking
 - d. Previous Hip Surgery

RECRUITMENT PROCEDURES

Patients will be recruited in the offices of the treating surgeon if they meet subject criteria, based on routine consultation. No active recruitment, such as advertisements, will be made. No compensation will be offered to participants.

DATA COLLECTION

Columbia University Medical Center will be used as a central location for data processing and management. Vanderbilt University, with collaboration from a consortium of institutional partners, has developed a software toolset and workflow methodology for electronic collection and management of research and clinical trial data. REDCap (Research Electronic Data Capture) data collection projects rely on a thorough study-specific data dictionary defined in an iterative self-documenting process by all members of the research team with planning assistance from the Biostatistics Unit of Columbia University Medical Center. The iterative development and testing process results in a well-planned data collection strategy for individual studies. REDCap servers are housed in a local data center at Columbia and all web-based information transmission is encrypted. REDCap has been disseminated for use locally at other institutions and currently supports 965 active institutional partners and other institutions in 78 countries (www.project-redcap.org).

INFORMED CONSENT

Patients willing to participate in the prospective study will be given written informed consent preoperatively. This will be performed by one of the investigators. Subjects will be informed that this study is being done to evaluate the potential effects of closed incision negative pressure therapy (ciNPT) on reduction of overall wound complications following direct anterior approach (DAA) total hip arthroplasty (THA) in high-risk patients compared to the standard dry dressing. Participating allows the researcher to use data from his/her medical record. No identifying information will be transmitted to other parties. Benefits and risks of participation will also be explained. Patients will also be given the option not to participate and receive routine care. Tests and treatment given will be a part of the standard of care and no extra procedures or treatments will be required for solely research purpose.

DISCOMFORTS AND RISKS

The Prevena Incision Dressing has an acrylic adhesive coating and a skin interface layer with silver, which may present a risk of an adverse reaction (redness, rash, itching, swelling or bruising) in patients who are allergic or hypersensitive to acrylic adhesives or silver. These risks are essentially identical to those seen with the control dressing. Please note that there is no evidence to support the risk of adverse skin reaction will be any higher than that of a traditional postoperative dressing. No additional risks to the standard care are anticipated for this study.

POTENTIAL BENEFITS

This includes improved wound healing from the use of the negative pressure dressing. The goal of this study is to determine if there is advantage of using this dressing on a routine basis compared to the standard dressing.

DEVICE PRECAUTIONS

Participants should contact the investigator in the event of visual or audible alerts as this may signal a leak, full canister, low battery, or device error. Participants need to remove the Prevena device prior to having a magnetic resonance imaging procedure or other diagnostic imaging procedures. The device should not be worn during hyperbaric oxygen therapy. Contact with the device must be avoided in the event of defibrillation or electrocardiograms.

DISCONTINUATION OF STUDY/SUBJECT WITHDRAWAL

Version Date: 10/22/12 Page 4 of 6

If subject wish to be withdrawn from the study at anytime, then they may do so and contact the surgeon investigators with this request. Subjects may also be withdrawn by the investigators for the follow reasons:

- failure to follow instructions,
- failure to show up for study visits,
- it is not in the subject's best interest to continue on this study, or
- the study is stopped.

ADVERSE EVENTS

Adverse events occurring as a result of experimental intervention is not anticipated. However, if such event does arise, this will be documented and written report will be given to the IRB and sponsor.

DATA AND SAFETY MONITORING

The Principal Investigator will be tasked with ensuring the safety of the study. The Principal Investigator will review the aggregate data every 6 months to determine if aspects of the study need to be changed or stopped. In addition, the Principal Investigator will review any and all deviations, adverse events and unanticipated problems that may occur to determine their relatedness to the study, their severity, and whether they require study changes. In addition, any unanticipated problems or instances of non-compliance will be reported to the IRB as per their reporting requirements. If any protocol changes are needed, the investigator will submit a modification request to the IRB. Protocol changes will not be implemented prior to IRB approval unless necessary to eliminate apparent immediate hazards to the research subjects. In such a case, the IRB will be promptly informed of the change following implementation.

CRITERIA FOR EVALUATING RESPONSE/STATISTICAL ANALYSIS

For the randomized control trial, a t-test for independent samples or a nonparametric Mann-Whitney U test will be used for determination of differences of mean values between the two treatment groups. The Kolmogorov-Smirnov test will determine the distribution form. For analysis of categorical data, a Fisher exact test will be used. The level of alpha will be set at p < 0.05.

REFERENCES/BIBIOGRAPHY

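### Envelope allocation has no stated concealment and no rule on when the arm is revealed, so the arm could be known before enrolment or during wound closure

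*Combined protocol and SAP*

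**What the plan says.** The allocation procedure is one phrase in Experimental Design: patients are assigned "using computer-generated, randomized envelopes with equal numbers in each treatment arm". The protocol does not say whether envelopes are sealed, opaque or numbered, who prepares, holds or opens them, whether blocks are used, or when an envelope is opened relative to consent, incision or closure.

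The setting is described elsewhere:

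- **Blinding (Experimental Design):** "neither patients nor treating surgeons can be blinded to treatment arm". The reason given is that the two dressings look different.
- **Timing of the intervention (Experimental Design):** "Both dressings will be applied under sterile conditions at the end of the DAA THA surgery, while still in the operating room".
- **Recruitment (Recruitment Procedures):** "Patients will be recruited in the offices of the treating surgeon if they meet subject criteria, based on routine consultation".
- **Consent (Informed Consent):** "Patients willing to participate in the prospective study will be given written informed consent preoperatively", and "This will be performed by one of the investigators".
- **Surgery (Inclusion and Exclusion Criteria):** "Patients undergoing primary THA through a direct anterior approach by one of the investigating surgeons".
- **Primary outcome (Experimental Design):** a wound complication counts when it needs intervention, and intervention covers anything the surgeon does to help the wound heal, from an ointment to a return to theatre.
- **Existing practice (Experimental Design):** ciNPT is already in selective use at the site for high-risk patients.

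**The concern.** Two routes to bias are left open.

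The first is at enrolment. If an envelope can be opened, or its content otherwise learned, before the patient is committed to the trial, whoever recruits can decide which patients enter which arm. The site already uses ciNPT selectively in high-risk patients, so a preference about who should receive it is plausible and need not be deliberate.

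The second is in the operating room. The dressing goes on only at the end of the operation, so nobody needs the assignment earlier. The stated reason for not blinding, the look of the dressings, does not apply until one is in place. Yet nothing delays the reveal. A surgeon who knows the arm may close the wound differently, and drainage and dehiscence, which closure could affect, are components of the primary outcome.

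Neither fault could be repaired afterwards. Intention-to-treat analysis takes the arms as they were formed, and masked reading of the photographs would not undo a selected sample or a different closure.

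**Working it through.** **1. The plan's own figure.** Inputs from Experimental Design: 34.5% against 11.5%, two-sided 0.05, Fisher's exact test, 58 per group, 80% power. Enumerating both binomials and summing the probability of all tables with p < 0.05 gives 79.5% power at 57 per arm and 80.5% at 58. The stated 116 reproduces and is not in dispute.

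**2. How far can the next assignment be guessed?** Assume the strictest reading, one list with exactly n = 58 per arm, and an observer who knows every past assignment and always guesses the arm with more places left. The expected number of correct guesses is

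n + (4^n / C(2n, n) − 1) / 2.

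With n = 58, 4^58 / C(116, 58) = 13.53, so the result is 58 + 12.53/2 = 64.3 of 116, or 55.4%. Chance gives 58 of 116. On average about 2 assignments at the end of the list are certain.

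The protocol mentions no blocks. If blocks of 4 were used and the size were known (both assumptions), the formula with n = 2 gives 2 + (16/6 − 1)/2 = 2.83 of 4, or 70.8%.

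**3. Can guessing alone bias the trial?** Suppose lower-risk patients are enrolled when one arm is guessed and higher-risk patients when the other is, and the two kinds differ in risk by D. The arms then differ by (2 × 0.554 − 1) × D = 0.108 × D.

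- For a 5-point shift, D = 0.05/0.108 = 46 points.
- For a 10-point shift, D = 0.10/0.108 = 93 points.
- With D = 20 points, the shift is 0.108 × 20 = 2.2 points, and the false-positive rate by the same Fisher enumeration is about 3.8%, still below 5%.

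Guessing from a single list therefore does little harm.

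**4. What would a given shift do, whatever its source?** Exact Fisher enumeration, 58 per arm, no true effect, starting from the protocol's 31% control rate. The shifts are assumed:

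| Risks in the two arms | p < 0.05 in either direction | p < 0.05 favouring the lower-risk arm |
|---|---|---|
| 31% / 31% (no shift) | 3.2% | 1.6% |
| 31% / 26% (5 points) | 6.4% | 6.1% |
| 31% / 21% (10 points) | 17.9% | 17.8% |

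Placing the shift elsewhere around 31% gives 6.1% to 6.4% at 5 points and 15.0% to 17.9% at 10 points. In the no-shift row, the last column is one direction only.

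**5. Knowledge before enrolment or closure.** No arithmetic applies. Consent is taken before surgery and the dressing is applied at its end. Between these points the protocol places no limit on when the envelope is opened, and before them it places none on access to the envelopes.

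**The case against.** The strongest reply is that this is silence rather than error. Sealed, opaque, numbered envelopes opened after closure would fit the protocol's wording, and the site may intend exactly that. This stands in part: the documents do not show that any envelope would be opened early or that any wound would be closed with the arm known. But the protocol does name a method, and it requires neither safeguard in a setting where the surgeons are unblinded and their decisions enter the endpoint.

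Several stronger readings are tempting and should not be drawn:

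- *That equal arms make allocation materially predictable.* Equal numbers may mean only a 1:1 ratio. Even a list fixed at 58/58 gives 55% correct guesses. The 71% figure needs blocks of 4 and knowledge of their size, and the documents mention neither. Both figures also need every past assignment to be known, whereas several surgeons may take part and the documents support such knowledge only for a surgeon's own patients.
- *That the 5- and 10-point shifts follow from guessing.* They do not. Step 3 shows the implausible risk differences this would need.
- *That one person recruits, consents, operates and judges the wound.* The protocol does not say so and names no wound assessor. It establishes only that the surgeon's intervention is part of the endpoint.
- *That a central randomisation system is already in place.* Data Collection says "Columbia University Medical Center will be used as a central location for data processing and management" and describes REDCap for data capture, not for allocation or use in the operating room. Well-run envelopes would also meet the concern.

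**Conclusion.** The concern holds as one about concealment and the timing of release. It is more than a request for detail, because withholding the assignment until the skin is closed is feasible, cheap and better than the procedure as written. It should be corrected, although nothing in the documents shows that bias would occur.

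Its size cannot be derived from the documents. Prediction from a single list is minor. For early opening and for closure with the arm known, the only figure available is conditional: an assumed 5-point shift would roughly double the false-positive rate, from 3.2% to about 6.4%, and take it past the planned 5%. For scale, the effect assumed in the sample size is 34.5 − 11.5 = 23 points. The illustration rests on 31% risk, 58 per arm, no true effect and the assumed shift. It is not a forecast.

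**What to change.** State in Experimental Design that:

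- someone independent of the surgeons generates and holds the allocation list;
- each assignment is released only after consent, registration and skin closure, with the time logged;
- any block sizes are not disclosed to the surgeons.

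A central electronic release is preferable, for example in REDCap if the site's set-up allows randomisation. Otherwise, use sealed, opaque, sequentially numbered envelopes held by non-surgeon staff and opened after closure.

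The cost is a small set-up task and a brief step in the operating room, with both dressings kept available until closure. The dressings, visits, sample size of 116 and analysis stay as they are. The change does not address who judges the outcome, which is a separate matter.

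### The healing-delay outcome has no stated population and no value for patients who heal on time; if only delayed patients are compared, a real benefit could be hidden or reversed

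*Combined protocol and SAP*

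**What the plan says.** The secondary outcomes are in the Combined protocol and SAP under EXPERIMENTAL DESIGN: "Secondary outcome measures will include duration of wound healing delay, length of hospital stay, number of days of antibiotic therapy", followed by costs. Nothing more is said about healing delay. There is no start point, no criterion for a healed wound, no value for a patient without delay and no analysis population.

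On observation, the same section says "Wounds will be assessed postoperatively at regular intervals until wound healing is achieved" and then "This will occur at least 2 and 6 weeks after surgery, which are standard intervals in our current postoperative protocol". It adds "No additional office visits will be needed for patients in the control or treatment arms" and, at the end of the section, "Patients will need to be followed for at least 90 days to assess postoperative wound healing complications".

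The section also commits to an intention-to-treat analysis. The one rule it gives for that, counting dropouts as failures, belongs to the yes/no primary outcome and has no meaning in days.

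Under CRITERIA FOR EVALUATING RESPONSE/STATISTICAL ANALYSIS, "a t-test for independent samples or a nonparametric Mann-Whitney U test will be used for determination of differences of mean values" between the arms, with a Kolmogorov-Smirnov test to judge the distribution. No method is named for an outcome that most patients may have at zero or not at all.

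**The concern.** A patient who heals without trouble has no delay to time. Taken literally, the outcome is therefore missing for most of both arms: 69% of controls and about 93% of ciNPT patients at the planning rates, if a complication is taken as a delay. The remaining patients were selected after randomisation by the process the dressing is meant to change. If ciNPT prevents the shorter problems, the few delayed patients left in its arm are the slow ones, and their average is longer although the arm as a whole has fewer days of delay.

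At stake is a secondary result of no difference, or of longer delay with ciNPT, that appears to contradict a favourable primary result. Because patients and surgeons know the allocation and the plan leaves both readings open, the choice between them could also be made after the data are known.

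**Working it through.** **Inputs from EXPERIMENTAL DESIGN.** Control complication rate 31%; effect factor 4.57; rates after 5% dropout 34.5% and 11.5%; 58 per arm; two-sided 0.05.

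**Assumptions not in the documents.** A complication stands in for a delay. Among delayed patients, delay is lognormal with median 14 days and log-SD 0.7; an exponential with mean 21 days is a second check. The 34.5% and 11.5% include dropouts, who have no measured delay, so that pair serves only as the other end of a range.

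**1. The plan's own figure.** 31%/4.57 = 6.8%. With dropouts as failures, 0.95 × 31% + 5% = 34.45% and 0.95 × 6.78% + 5% = 11.44%, which match the stated rates to rounding. Exact Fisher power at 34.5% versus 11.5% is 79.5% with 57 per arm and 80.5% with 58. The planned 116 is reproduced. No figure is stated for the delay outcome.

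**2. Patients with a delay.**
- At 31% versus 6.8%: 0.31 × 58 = 18.0 and 0.0678 × 58 = 3.9.
- At 34.5% versus 11.5%: 0.345 × 58 = 20.0 and 0.115 × 58 = 6.7.

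**3. Simulation, lognormal delays, 4,000 trials per row.** Three ways in which ciNPT might prevent delays: regardless of length; mixed (half of the prevented delays are the shortest ones, the rest taken at random); only the shortest. Each cell gives the result at 31% versus 6.8%, then at 34.5% versus 11.5%.

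| Delays prevented | Delayed only: ciNPT mean longer | Delayed only: Mann-Whitney significant, ciNPT longer | Delayed only: Mann-Whitney significant, ciNPT shorter | All randomised with zeros: Mann-Whitney finds benefit | All randomised with zeros: t-test finds benefit |
|---|---|---|---|---|---|
| Any length | 41%, 47% | 2%, 2% | 2%, 2% | 94%, 84% | 80%, 64% |
| Mixed | 74%, 80% | 15%, 20% | 0%, 0% | 91%, 79% | 64%, 47% |
| Shortest only | 92%, 98% | 70%, 77% | 0%, 0% | 89%, 73% | 33%, 23% |

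At 31% versus 6.8%, the delayed-only test could not be run in 8 to 9% of trials because an arm had fewer than two delayed patients. Over all randomised patients, the rank test was significant in the wrong direction in 0.0% of trials in every row.

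**4. Second distribution, exponential with mean 21 days, 31% versus 6.8%, 3,000 trials.** Mean delay per randomised control is 0.31 × 21 = 6.5 days.
- *Prevention regardless of length.* The ciNPT mean per randomised patient is 0.0678 × 21 = 1.4 days. The delayed-only test is significant in 4% of trials, either direction; the all-randomised rank test is significant in 94%.
- *Prevention of only the shortest.* The mean among delayed ciNPT patients is 21 × (1 + ln 4.57) = 52.9 days, against 21 in controls. The ciNPT mean per randomised patient still falls, to 0.0678 × 52.9 = 3.6 days. The delayed-only test shows significant harm in 67%; the all-randomised rank test favours ciNPT in 89%.

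**5. Visit spacing.** The lognormal simulation was repeated with delay recorded only at days 14, 42 and 90. Significant apparent harm in the shortest-only case was 59% and 37%, lower than with exact dates. The all-randomised rank test kept 81 to 94% power across all cases. Coarse timing does not create the reversal.

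**The case against.** The strongest reply is that nothing in the documents limits the comparison to delayed patients. Intention to treat is stated, and the test is described as one "will be used for determination of differences of mean values between the two treatment groups", which reads naturally as the randomised arms. With zero days for on-time healers the reversal disappears and the plan's own Mann-Whitney option works well. This stands, and it rules out saying that the plan specifies a delayed-only analysis. It does not close the gap, because the zero is never stated and the only intention-to-treat rule given cannot be applied to days.

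A reader might also infer that the schedule is to blame, since a wound open at week 2 and closed at week 6 has a healing date known only to within 42 − 14 = 28 days. The documents do not support this as a general statement. Weeks 2 and 6 are minimum visits, assessment continues until healing, follow-up is at least 90 days, and interventions such as in-office debridement are themselves contacts. The 28 days applies only where no one sees the wound in between.

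The t-test criticism is limited too. With this many zeros, the distribution check would probably lead to Mann-Whitney.

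Finally, the largest reversal figures need ciNPT to prevent only the shortest delays, and every duration figure rests on an assumed distribution. Both points are fair.

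**Conclusion.** The concern holds in a limited form. The outcome is undefined in the two respects that decide whether the comparison is randomised: who is included, and what an on-time healer scores. On the ordinary meaning of the words, about 18 control and 4 ciNPT patients would be compared. A true benefit would then usually appear as no difference, and as significant harm in about 15 to 20% of trials in the mixed case and about 70 to 77% in the extreme case. On the zero-delay reading a rank test finds the benefit in about 73 to 94%.

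The direction of these results agrees under both assumed distributions; the exact percentages should not be relied on, and all of them take a complication as a delay. It would go too far to conclude that the planned analysis will mislead, or that ciNPT would have helped every patient in such a trial: most patients have no delay to shorten, and in the extreme case those with long delays gain nothing. Only the arm average falls.

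This is a secondary outcome that does not appear in the null hypotheses. The primary analysis and N = 116 are untouched. It is still worth settling before analysis, because the two permissible readings can give opposite answers.

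**What to change.** In EXPERIMENTAL DESIGN, define days of healing delay for every randomised patient, with a start point and a healed criterion chosen by the investigators, and score on-time healing as 0. In the statistical section, compare all 116 patients by intention to treat with a Mann-Whitney test and drop the t-test for this outcome. State how patients who drop out or are unhealed at the end of follow-up are ranked, since the existing dropout rule covers only the primary outcome. Report duration among delayed patients descriptively, without a test. Count antibiotic days over all randomised patients in the same way, with zeros.

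Where no assessment falls between two visits, treat the healing date as interval-censored.

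Replacing days with three categories (healed by week 2, healed by week 6, not healed) is not a safe shortcut. With the exponential assumption at 31% versus 6.8%, its power is about 65% (prevention regardless of length) and 30% (shortest only) if delay is counted from surgery, and about 93% and 90% only if it is counted from day 14. The start point therefore has to be written down in any case.

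The cost is wording: no extra visits and no change to the primary analysis or N. The downside is that the mean number of days among delayed patients is no longer a tested result.
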